Overall, the cediranib/olaparib combination demonstrated a significant clinical benefit over olaparib alone, as measured both by PFS and ORR. The increased clinical benefit of the cediranib/olaparib combination over olaparib monotherapy was greater in women with tumors that were not *gBRCAm* or who had a VUS status compared with women who harbored *gBRCA1/2* mutations. Toxicities were consistent with expected class-related toxicities of these drugs, with most common grade 3 or 4 toxicities attributed to each of the IPs including fatigue (27% cediranib/olaparib vs. 11% olaparib), diarrhea (23% vs. 0%), and hypertension (41% vs. 0%). There were 2 Common Terminology Criteria for Adverse Event (CTCAE) Grade 4 events, both in the cediranib/olaparib arm: 1 event of Grade 4 hypertension in a patient who was not fully compliant with blood pressure (BP) monitoring and 1 event of Grade 4 myelodysplastic syndrome (MDS).

Summaries of the clinical data in patients with recurrent ovarian cancer for cediranib/olaparib combination compared with single agent olaparib or cediranib are shown in [Table 3](#) and [Table 4](#), respectively.

Table 3 Comparison of cediranib/olaparib and single-agent olaparib in recurrent ovarian cancer trials

Patient characteristics	Treatment	Number of patients	PFS (months)	ORR (%) by RECIST	Reference
gBRCAm (N=47);	Olaparib single agent 400 mg bd	46	9.0	56.1	Liu et al 2014
gBRCAwt (N=43) all platinum-sensitive	Cediranib 30 mg od plus olaparib 200 mg bd	44	17.7	83.7	
all gBRCAm ; all partially platinum sensitive	Olaparib 200 mg bd	32	6.5	25	Kaye et al 2012
	Olaparib 400 mg bd	32	8.8	31	
	PLD 50 mg/m ²	33	7.1	18	
gBRCAm (N=17); non- gBRCAm (N=46)	Olaparib 400 mg bd; platinum-sensitive patients	25	N/A	52	Gelmon et al 2011
	Olaparib 400 mg bd; platinum-resistant patients	38	N/A	13	
	Olaparib 400 mg bd; platinum resistant (non- gBRCAm only)	26	N/A	4	

Abbreviations: bd twice daily; *gBRCAm* germline *BRCA* mutant; *gBRCAwt* germline *BRCA* wild type; N/A not available; N number of subjects; od once daily; ORR objective response rate; PFS progression free survival; PLD Pegylated liposomal doxorubicin; RECIST Response Evaluation Criteria in Solid Tumors; VUS variant of unknown significance.

Note: these studies used the capsule formulation of olaparib.

Table 4 Comparison of cediranib/olaparib and single-agent cediranib in recurrent ovarian cancer trials

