3.9 Discontinuation of investigational product

Patients may be discontinued from IPs in the following situations:

- Patient decision; the patient is at any time free to discontinue treatment, without prejudice to further treatment. A patient who discontinues treatment is normally expected to continue to participate in the study unless she specifically withdraws her consent to further participation in any study procedures and assessments (see Section 3.10.1).
- Adverse Event (AE), including AEs that meet criteria for discontinuation as defined in Section 6.7; any AEs that, in the opinion of the Investigator or AstraZeneca, contraindicates further dosing.
- Objective progression according to RECIST version 1.1 criteria.
 - Severe non-compliance with the protocol

Both IPs (cediranib and olaparib) should be discontinued at the same time; patients are not allowed to remain in the study if they are taking either cediranib or olaparib as monotherapy.

However, in rare circumstances, patients experiencing ongoing clinical benefit but who develop one of the toxicities listed below, related to one of the IPs, that prevents them to continue to take this IP, may be allowed to continue on the unrelated drug if in the opinion of the treating investigator the risk benefit remains favorable and only after discussion with the AstraZeneca Study Physician and the Principal Investigator.

AEs requiring cediranib to be discontinued:

- GI perforation
- Arterial Thromboembolic Event
- Reversible Posterior Encephalopathy Syndrome (PRES)
- Severe hemorrhage
- Severe persistent hypertension despite maximal anti-hypertensive treatment

AEs requiring olaparib to be discontinued:

- Bone marrow findings consistent with MDS/AML.
- Severe persistent anemia
- Pneumonitis

Refer to Section 6.7 for more information on the management of IP-related toxicities.

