6.8 Management of IP related toxicities

The dose levels and the general approach to dose modification of the cediranib and olaparib component of the combination therapy are shown in Table 7 and Table 8, respectively. Specific dose modification information for some AEs are provided in Section 6.8.3 and Section 6.8.4. Please refer to the current IBs for emerging safety data for cediranib and olaparib: CCI

AEs should be treated with the appropriate maximum supportive care, and dose reductions should be clearly documented in the eCRF.

Table 7 Dose modification cediranib

Dose Level	Cediranib tablets
Initial dose	30 mg daily
Dose reduction 1	20 mg daily
Dose reduction 2	15 mg daily

Table 8 Dose modification of olaparib

Dose Level	Olaparib tablets
Initial dose	200 mg twice daily
Dose reduction 1	150 mg twice daily
Dose reduction 2	100 mg twice daily

At the discretion of the investigator, the study drugs may be held or dose modified independently if the observed toxicity is attributed to only one of the drugs, while the patient continues to receive the drug not associated with the observed toxicity. The time a given drug is held should not exceed 3 weeks. Once dose of study drug(s) have been reduced, no dose re-escalation is permitted.

If treatment has to discontinue due to toxicity, both IPs (cediranib and olaparib) should be discontinued at the same time; patients are not allowed to remain in the study if they are taking either cediranib or olaparib as monotherapy. However, in rare circumstances, patients experiencing ongoing clinical benefit but who develop one of the toxicities listed below related to one of the IPs that prevents them to continue to take this IP, may be allowed to continue on the unrelated drug if in the opinion of the treating investigator the risk benefit remains favorable and only after discussion with the AstraZeneca Study Physician and the Principal Investigator.

AEs requiring cediranib to be discontinued:

- GI perforation
- Arterial Thromboembolic Event
- PRES
- Severe hemorrhage
- Severe persistent hypertension despite maximal anti-hypertensive treatment

AEs requiring olaparib to be discontinued:

- Bone marrow findings consistent with MDS/ AML
- Severe persistent anemia
- Pneumonitis

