Patients experiencing ongoing clinical benefit who experience a related AE where continuation of one of the drugs is considered, in the judgment of the treating Investigator AND the Principal Investigator, to be potentially life threatening or with the potential for long-term harm to the patient, may be allowed to continue on the unrelated drug after discussion with the AstraZeneca Study Physician and the Principal Investigator.

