6.8.2 Non-hematologic toxicity

Cediranib should be discontinued should any of the following AEs occur: GI perforation; arterial thromboembolic events; PRES (radiologically confirmed); severe or medically significant hemorrhage and severe persistent hypertension despite maximal anti-hypertensive treatment.

Dose modifications for other non-hematologic events on IPs should be managed according to Table 11.

Table 11 General Management of Non-Hematologic Toxicity

Observation	Action
AE resolves promptly with supportive care	Maintain dose level
Any \geq Grade 3 non-hematologic (excluding grade 3 fatigue or easily correctable asymptomatic grade 3 laboratory abnormalities)	Hold IP(s) ^a for up to 3 weeks until toxicity resolves to \leq Grade 1. Treatment may be restarted at one dose level lower for the IP(s) causing the toxicity (see Table 7 and Table 8), at the treating investigator's discretion ^b . Reoccurrence of Grade 3 or 4 toxicity would require dose reduction of both IPs.
Any grade 2 non-hematologic AE or grade 3 fatigue related to cediranib or olaparib that persists despite maximal support.	Hold IP(s) ^a for up to 3 weeks until toxicity resolves to Grade ≥ 1 . Treatment may be restarted at one dose level lower for the IP(s) causing the toxicity (see Table 7 and Table 8), at the treating investigator's discretion ^b .
Grade 3 or 4 non-hematologic AE related to cediranib and olaparib combination that does not resolve to Grade 0-2 within 3 weeks despite maximum supportive care after treating patient at the lowest reduced dose level ^c	Discontinue IP(s)

a. At the discretion of the investigator, one IP may be held or dose modified or discontinued independently if the observed toxicity is attributed to only one of the drugs, while the patient continued to receive the second drug not associated with the observed toxicity. The time a given drug is held should not exceed 3 weeks.

- b. Patients who are at the lowest reduced dose level may have their drug resumed at that dose level after discussion with the AstraZeneca Study Physician and the Principal Investigator if evidence of clinical benefit.
- c. For venous thromboembolic events, treatment may be resumed at the discretion of the investigator once patient is asymptomatic (Section 6.7.3.11).

Abbreviations: AE adverse event; IP investigational product(s)

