6.8.3.2 Diarrhea

Diarrhea is often observed with cediranib. Diarrhea usually starts early (within the first 4 weeks of treatment), however, it can occur at any time during treatment. Management of diarrhea should start at the first sign of diarrhea. Loperamide and advice on how to manage diarrhea should be readily available to patients from the start of cediranib treatment so that they can be applied at first episode of diarrhea. Active and early management of diarrhea is recommended even with Grade 1 diarrhea. Management is as shown in Table 13:

Table 13 Management of Diarrhea

Toxicity	Management/Modifications
Initial grade 1 or 2 diarrhea	
Patients should start loperamide (per standard practice) and continue to take loperamide until patients are free from diarrhea for at least 12 hours. The dose of loperamide should not exceed 16 mg in a 24-hour period. Patients should also be counselled to start a BRAT diet.
 
If diarrhea persists despite 24 hours of loperamide treatment, withhold cediranib for a maximum of 7 days, continue loperamide, and maintain hydration. Cediranib may be restarted at the same dose once patients have been free from diarrhea for 12 hours.
 
Patients should be instructed to contact their study physician if mild or moderate (NCI CTCAE Grade 1 or 2) diarrhea persists for over 48 hours despite treatment with loperamide and cediranib dose interruption.

Table 13 Management of Diarrhea

Toxicity	Management/Modifications
For either persistent grade 2 diarrhea or grade 3 or 4 diarrhea	Patients with persistent or severe diarrhea (NCI CTCAE Grade 3 or higher) may also require dose reduction or discontinuation of therapy with cediranib, follow guidance in Table 7

Abbreviations: BRAT bananas, rice, applesauce, toast; CTCAE Common Terminology Criteria for Adverse Event; NCI National Cancer Institute.

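### Table 11 footnote a lets the investigator alone stop one drug for good and continue the other, against the both-stop rule in the synopsis, Section 3.9 and Section 6.8

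*Protocol*

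**What the plan says.** Protocol Section 6.8 treats two actions differently.

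- **Holding or reducing one drug.** This is left to the investigator: "the study drugs may be held or dose modified independently if the observed toxicity is attributed to only one of the drugs". The other drug continues, and a hold should not exceed 3 weeks.
- **Discontinuing for toxicity.** The rule is "If treatment has to discontinue due to toxicity, both IPs (cediranib and olaparib) should be discontinued at the same time", and monotherapy patients may not remain in the study. The synopsis (Duration of treatment) and Section 3.9 also require both drugs to stop together and bar monotherapy.

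There are two exceptions to the discontinuation rule.

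- **Listed events** (synopsis, 3.9, 6.8). In rare circumstances, a patient with ongoing clinical benefit and one of eight listed adverse events (five for cediranib, three for olaparib) may stay on the unrelated drug. Section 3.9 allows this if the treating investigator considers that the "risk benefit remains favorable and only after discussion with the AstraZeneca Study Physician and the Principal Investigator".
- **Serious harm** (end of 6.8). A patient with ongoing benefit may continue the unrelated drug after a related event for which the treating investigator and the Principal Investigator both judge continuing one of the drugs "to be potentially life threatening or with the potential for long-term harm to the patient". The same discussion is required.

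Table 11 in Section 6.8.2 covers the non-haematologic events that remain after the five cediranib-stopping events are set aside. Its footnote a says that, at the investigator's discretion, "one IP may be held or dose modified or discontinued independently if the observed toxicity is attributed to only one of the drugs". The patient then stays on the other drug.

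**The concern.** Footnote a moves permanent discontinuation of one drug from the restricted category in Section 6.8 to the investigator's sole discretion. Its only condition is that the toxicity is attributed to one drug. It requires no listed event, ongoing benefit, harm threshold or discussion.

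At stake is a treatment instruction: may a patient stay on a single agent, and who has to agree? Section 1.2 justifies testing only the combination because the single agents have limited activity in platinum-resistant disease. It cites olaparib 4% (1/26) in patients without a *BRCA* mutation, and cediranib 17% in one study and 0% (0/35) in another. A site that relies on footnote a would keep a patient on such a drug without the sponsor's physician or the Principal Investigator being consulted.

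**Working it through.** No arithmetic applies to the conflict itself. The check is a comparison of the texts.

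| Place (Protocol) | Action on one drug alone | Who decides | Conditions |
|---|---|---|---|
| 6.8, hold sentence | Hold or dose modify | Investigator | Toxicity attributed to one drug; hold up to 3 weeks |
| Synopsis, 3.9, 6.8 | Discontinue, continue the other | Treating investigator, after discussion with sponsor physician and Principal Investigator | Rare; ongoing benefit; one of eight listed events; favourable risk-benefit |
| 6.8, closing paragraph | Discontinue, continue the other | Treating and Principal Investigator, after the same discussion | Ongoing benefit; life-threatening or long-term harm |
| Table 11 footnote a | Hold, dose modify **or discontinue**, continue the other | Investigator | Toxicity attributed to one drug; the 3-week limit concerns holds |

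**Step 1: what differs.** Footnote a is close to the hold sentence in Section 6.8. The difference that matters is the added words *or discontinued*.

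**Step 2: is the discussion implied?** No. Footnote b of the same table requires discussion with the sponsor physician and the Principal Investigator before a drug is resumed at the lowest dose level. Section 6.8.3.1 requires it when hypertension delays dosing by more than 3 weeks. Table 12 requires it before cediranib is resumed after life-threatening hypertension. Where the authors wanted the discussion, they wrote it.

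**Step 3: which events are reached?** The footnote marker sits on two rows: grade 3 or higher non-haematologic events, and grade 2 events or grade 3 fatigue that persist despite maximal support. Table 11 excludes the five listed cediranib events, and two of the three listed olaparib events are haematologic. Apart from pneumonitis, then, footnote a applies to events outside the Section 6.8 list. A persistent grade 2 event is also unlikely to meet the serious-harm route. So the footnote grants most where Section 6.8 allows least.

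**Step 4: does the plan foresee stopping one drug for unlisted events?** Yes. Table 13 says that patients with persistent or severe diarrhoea "may also require dose reduction or discontinuation of therapy with cediranib". Stopping cediranib is to be considered for fistula (6.8.3.9) and may be considered for venous thromboembolism (6.8.3.11). Stopping olaparib is recommended for severe renal impairment (6.8.4.4). None of these sections says what happens to the other drug.

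**Step 5: one patient, two sites.** Take a patient with ongoing benefit who develops a fistula attributed to cediranib, and cediranib is stopped. Under footnote a, the site may continue olaparib on its own decision. Under Section 6.8, both drugs stop unless the serious-harm route is met and discussed.

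**Step 6: endpoints.** Time to treatment discontinuation or death ends at the earliest date on which either drug is discontinued (Protocol 8.4.2, SAP 3.2.2), so the conflict does not change how it is derived. A confirmed response counts unless it occurred or was confirmed after further anticancer therapy (Protocol 8.4.1, SAP 3.2.1). Stopping one study drug does not by itself exclude a later response.

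**The case against.** The strongest reply is that this is a drafting slip with little reach. The marker sits on the two hold rows and not on the discontinue row. The footnote ends with a limit on holds. Three other places state the both-stop rule plainly. For diarrhoea, Table 13 refers to Table 7, which is in Section 6.8 beside the both-stop rule, so a site following it is not led to footnote a. All of this is fair. It makes a slip likely and weakens diarrhoea as an example of footnote a in use. It does not remove the permission: the sentence expressly allows discontinuation, and a site using Table 11 may act on it.

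A second reply is that the SAP already makes such patients largely visible. Section 4.2.6 summarises exposure for each drug and for the combination, and plots two dose bars per patient. Section 4.2.9 reports adverse events leading to discontinuation of either drug separately. Section 2.2 provides for review of monitoring notes for deviations that programming cannot find. This stands. What is not specified is a record of whether an exception was agreed.

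A reader might go further and infer that responses on a single drug could lift the primary result over the plan's 90% criterion. With the planned Beta(1/3, 1/3) prior and 60 patients, the posterior probability that ORR is at least 20% is 0.894 at 16 responders and 0.939 at 17. The documents do not support that inference, for four reasons.

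- **Dual criterion.** Protocol 8.2 also asks for 30/100 observed, and both parts were set for 100 patients. No threshold is restated for 60. If 30% is carried over, 17/60 = 28.3% still fails, and 18/60 = 30% already has a probability of 0.967.
- **No usable rate.** A count of affected patients would have to borrow toxicity stops from single-agent cediranib studies, some of which may have been for listed events. No corresponding rate is given for olaparib. The single-agent response rates run from the start of treatment, not from a switch after combination exposure.
- **Attribution.** With scans every 8 weeks, a response first seen after one drug stopped may reflect earlier combination treatment.
- **Not specific to footnote a.** The same counting applies to properly agreed exceptions. It also applies to patients who stop both drugs without progression and continue scans (3.9.1, 4.3.2).

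**Conclusion.** The conflict is real and stands in the operative text of protocol version 5.0. Footnote a gives the investigator sole authority to discontinue one drug and continue the other. The synopsis, Section 3.9 and Section 6.8 withhold that authority, and no other text reconciles them. It should be corrected because it is a contradictory dosing instruction that decides whether a patient stays on one drug of low expected activity without sponsor review.

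Its frequency cannot be derived from the documents. Grade 3 or 4 diarrhoea was reported in 23% of the combination arm of the Phase II study (Section 1.1.4.3), but the protocol does not say how many of those patients stopped a drug. The effect on ORR cannot be quantified either and is likely small. The conclusion rests on the wording alone and needs no assumption about response or stopping rates.

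**What to change.** 1. In Table 11 footnote a, delete *or discontinued*, so that it covers the same actions as the hold sentence in Section 6.8. Add: *If one IP has to be permanently discontinued, both IPs stop unless an exception in Section 6.8 is agreed.*
2. Put the same pointer in the severe-diarrhoea row of Table 13.
3. Optionally, list in the study report the patients who continued on one drug, with the stop date, the reason and whether the exception was agreed.

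The cost is two short wording edits and a letter to sites. For the optional listing, dosing and discontinuation dates and the action taken for each drug are already collected (Protocol 6.3.4, SAP 3.2.2, 3.3.1 and 3.3.3). Whether an exception was agreed would have to come from study correspondence or monitoring notes. No change to the primary analysis or its sensitivity analyses is needed.

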6.8.3 Management of cediranib-related toxicity

6.8.3.1 Hypertension

Only doses of cediranib will be modified for hypertension; olaparib doses will not be reduced unless other toxicities are experienced.

In clinical trials, increases in BP have been reported within a few hours of starting cediranib. Since rapid changes in blood pressure can occur with cediranib treatment, with the potential for life-threatening complications if hypertension is not appropriately managed, all patients should check their BP twice daily for at least the first 8 weeks after starting cediranib, or, if antihypertensive management is required, until a stable anti-hypertensive regimen has been established, even if this requires more than 8 weeks. After 8 weeks or once a stable regimen has been achieved, BP monitoring may be reduced to once daily. Twice daily monitoring should be re-implemented after any cediranib dose interruption for 2 weeks or until the patient is re-established on a stable antihypertensive regimen, whichever takes longer.

Patient BP will also be measured during routine study visits: weekly during the first 4 weeks, every 2 weeks during the next 4 weeks and every 4 weeks thereafter, to ensure that BP guidelines are being correctly followed. Increase in BP should be treated promptly with standard antihypertensive therapy, ensuring that the maximum recommended dose and number of antihypertensive medicinal products is reached before considering cediranib dose adjustment. See Appendix G for suggested antihypertensive medications by class. Patients may have up to 4 drugs for management of hypertension prior to any dose reduction in cediranib.

If patients require a delay of > 3 weeks for management of hypertension, discontinuation of cediranib or protocol therapy may be considered after discussion with the PI and the AstraZeneca study physician. In case of persistent or severe hypertension, despite the optimal use of antihypertensive medicinal products and cediranib dose reduction, cediranib should be permanently discontinued.

Patients already taking antihypertensive therapy at baseline or those aged 75 years or older are at a higher risk of having elevated BP or may require more than one medicinal product or more intensive therapy. Pre-existing cardiovascular risks should be assessed and managed, and pre-existing hypertension should be adequately controlled before starting treatment with cediranib. Note: Stopping or reducing the dose of cediranib is expected to cause a decrease in BP. The treating physician should monitor the patient for hypotension and adjust the number and dose of antihypertensive medications accordingly.

Hypertension should be graded using the NCI CTCAE version 4.03. Please note: patients may have baseline hypertension meeting CTCAE grading criteria on study entry provided this is adequately controlled on maximum of 3 antihypertensive medications (see Section 3.1).

Baseline grade of hypertension should also be recorded in Medical History eForm.

Should patients require increase in dosing of BP medication or increased number of medications, they should then be noted to have hypertension related to study drug, with grading as per CTCAE version 4.03 criteria.

Table 12 provides hypertension monitoring and management guidance.

Table 12 Hypertension Monitoring and Management

Event	Antihypertensive Therapy	Blood Pressure Monitoring	Cediranib Dose Modification
Asymptomatic transient (<24 hours) increase by >20 mmHg diastolic or to >140/90 mmHg if previously within normal limits	Consider early initiation of BP medication for BP > 140/90 mmHg that is confirmed on a second reading. Cediranib can cause rapid escalation in BP, and early initiation of BP management can reduce likelihood of hypertension-related complications	Continue standard BP monitoring according to local practice and confirm resolution of BP to <140/90 mmHg within 24 hours.	None

Table 12 Hypertension Monitoring and Management

Event	Antihypertensive Therapy	Blood Pressure Monitoring	Cediranib Dose Modification

Recurrent or persistent (>24 hours) or symptomatic increase by >20 mmHg (diastolic) or to > 140/90 mmHg if previously within normal limits.
 
Monotherapy may be indicated
	
Initiate BP medication for first line treatment. Suggestions: ACE inhibitor or Calcium Channel Blocker
 
Escalate dose of medication in step wise fashion until BP is controlled or at a maximum dose
 
If BP is not controlled to <140/90 mmHg with one “maximized” drug regimen, then add a second agent.
 
Study drug does not need to be held unless otherwise clinically necessary
 
Consider renal consult
	
Increase frequency of monitoring until stabilized to BP <140/90 mmHg
	
Do not withhold cediranib unless otherwise clinically necessary

Table 12 Hypertension Monitoring and Management

Event	Antihypertensive Therapy	Blood Pressure Monitoring	Cediranib Dose Modification
Requiring more than one drug or more intensive therapy than previously.	
Maximize 2 drug regimen
 
Suggestions: ACE-inhibitor + Calcium Channel Blocker
 
Escalate doses of existing medication until BP is controlled or at a maximum dose.
 
If BP is not controlled to <140/90 mmHg with two drug regimen, then add a third agent.
 
Study Drug will not be held during trial of two drug combinations. Additional antihypertensive drugs, up to a total of 4, may be maximized for BP control.
 
Consider consult with a BP management specialist if greater than 3 drugs are required for BP control.
	Increase frequency of monitoring until stabilized to BP <140/90 mmHg	
Do not withhold cediranib unless BP is not decreased to less than 150/100 mmHg 48 hours after multi-drug therapy is instituted or if clinical symptoms worsen (eg, headache).
 
If BP is not controlled to less than 150/100 mmHg with maximal therapy or if clinical symptoms worsen, then withhold cediranib (up to 3 weeks) until maximum effect of the antihypertensive agents is achieved.
 
If BP is reduced to Grade 1 within 3 weeks, cediranib may be resumed at prior dose.

Table 12 Hypertension Monitoring and Management

Event	Antihypertensive Therapy	Blood Pressure Monitoring	Cediranib Dose Modification
If threatening consequences OR SBP \geq 180mmHg OR DBP \geq 110mmHg	Initiate treatment Hospitalize patient for ICU management, IV therapy as necessary. 14 days are allowed to maximize the full effect of anti-hypertensive agents.	Intensive BP monitoring (hospitalization if necessary)	Withhold cediranib. If BP is reduced to Grade 1 within 3 weeks, cediranib may be resumed at a reduced dose after discussion with the AstraZeneca Study Physician and the Principal Investigator.

Abbreviations: ACE Angiotensin Converting Enzyme; BP blood pressure; DBP diastolic blood pressure; ICU intensive care unit; IV intravenous; SBP systolic blood pressure.

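### Section 6.8.3.1 lets a cediranib hold for hypertension run past the 3-week limit set in Section 6.8, Table 11 and Table 12, and the sections also differ on when cediranib must stop

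*Protocol*

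**What the plan says.** Section 6.8, the general rule for toxicity, lets the investigator hold one drug while the other continues, with a limit: "The time a given drug is held should not exceed 3 weeks". Footnote a of Table 11 (Section 6.8.2) repeats that limit for non-hematologic toxicity.

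Table 12, inside Section 6.8.3.1, covers hypertension. In the row for patients who need more than one antihypertensive drug, if blood pressure stays uncontrolled on maximal therapy or symptoms worsen, the site is to "then withhold cediranib (up to 3 weeks) until maximum effect of the antihypertensive agents is achieved". Cediranib may be resumed at the prior dose if Grade 1 is reached within 3 weeks. The most severe row also gives 3 weeks to reach Grade 1, with resumption at a reduced dose after discussion.

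The running text of Section 6.8.3.1 says: "If patients require a delay of > 3 weeks for management of hypertension, discontinuation of cediranib or protocol therapy may be considered". That sentence requires discussion with the PI and the study physician. The next one deals with persistent or severe hypertension: "despite the optimal use of antihypertensive medicinal products and cediranib dose reduction, cediranib should be permanently discontinued".

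Sections 3.9, 6.8 and 6.8.2 (and the synopsis) carry a separate list of events that require cediranib to stop. It includes hypertension that is severe and persistent although antihypertensive treatment is at its maximum. The list does not mention a prior cediranib dose reduction and gives no duration.

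**The concern.** A site with a patient whose blood pressure is still uncontrolled at the end of the third week of a hold finds different answers in different places. The general rule and Table 12 say the hold has reached its limit. The text above Table 12 says a longer delay is possible and that stopping is something to consider. The mandatory-stop sentences depend on which section is read, and the phrase covering cediranib or protocol therapy leaves open whether one drug or both would stop.

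The first stake is patient safety. Section 6.8.3.1 itself describes inadequately managed hypertension as potentially life-threatening, and Sections 4.5 and 9.3 keep the stopping criteria in force for patients treated beyond the Final Protocol Visit. The second stake is smaller: the date and occurrence of a cediranib discontinuation feed TDT and the exposure tables.

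**Working it through.** The plan gives no figure to reproduce and no arithmetic settles the point, so the check is a comparison of texts.

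**Length of a cediranib hold**

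| Place in protocol | Hold length | Action if not resolved |
|---|---|---|
| Section 6.8 | not more than 3 weeks | none stated at the limit |
| Table 11, footnote a | not more than 3 weeks | none stated in the footnote |
| Table 12, multi-drug row | up to 3 weeks | none stated |
| Table 12, most severe row | 3 weeks to reach Grade 1 | none stated |
| Section 6.8.3.1, text | more than 3 weeks foreseen | stopping cediranib or protocol therapy considered, after discussion |

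Four places work to 3 weeks and one goes beyond it. The exception sits in the same section as two of the four, so Section 6.8.3.1 disagrees with its own table.

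**Mandatory stop for hypertension**

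| Place in protocol | Severity condition | Antihypertensives at maximum or optimum | Dose reduction mentioned | Duration |
|---|---|---|---|---|
| Sections 3.9, 6.8, 6.8.2 | severe and persistent | yes | no | none |
| Section 6.8.3.1, text | persistent or severe | yes | yes | none |

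**One patient through both tables.** Take a patient at the initial cediranib dose, in the multi-drug row, on maximal antihypertensive therapy, on hold and uncontrolled on day 22 (3 × 7 = 21 days have passed).

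1. Section 6.8 and Table 11, footnote a: the hold is over its limit.
2. Table 12: the permitted hold has ended. Resumption requires Grade 1, which she has not reached, and no other branch is given.
3. Section 6.8.3.1, delay sentence: the hold may go on, with stopping considered.
4. Sections 3.9, 6.8 and 6.8.2: if her hypertension is judged severe and persistent, cediranib must stop.
5. Section 6.8.3.1, mandatory-stop sentence: on a literal reading it is not met, because no dose reduction has been made. She can reach this point without one, since this row resumes at the prior dose.

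She may therefore be over the cap, at a mandatory stop, or eligible for a continued hold, depending on the text followed.

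Elsewhere the protocol does state what happens at 3 weeks. Section 6.8.1.3 stops both drugs if blood counts have not recovered. Section 6.8.5 sends non-toxicity interruptions to the study physician.

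**Reach into the analysis.** Where one drug stops before the other, TDT runs to the earliest discontinuation date (Protocol 8.4.2, SAP 3.2.2). Stopping cediranib is then an event, while a continued hold followed by resumption is not. If cediranib stops during a hold, SAP 3.3.1 uses the date of last administration. Under that rule a stop declared on day 22 of the hold and one declared later in the same hold carry the same date. The rule sits in the exposure section, and the TDT definition does not repeat it. Interruption counts and durations (SAP 4.2.6) change with the length of the hold. The primary ORR is not defined by any of these rules.

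**The case against.** The strongest defence is that the specific rule governs the general one. Section 6.8 says "Specific dose modification information for some AEs are provided in Section 6.8.3 and Section 6.8.4", so Section 6.8.3.1 could be an intended exception for hypertension. A delay beyond 3 weeks is also not left to the site alone, because it requires discussion with the PI and the study physician, and a mandatory stop for persistent or severe hypertension follows in the next sentence. On this view the 3-week figure is a working limit and Section 6.8.3.1 says what to do when it is passed.

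The safeguards are real, and they rule out describing the hold as unsupervised. The defence does not remove the contradiction. Nothing says that the cap is lifted for hypertension, and Table 12, which belongs to the specific section, keeps the 3 weeks. Section 6.8.2 adds "Dose modifications for other non-hematologic events on IPs should be managed according to Table 11", which can bring hypertension short of a mandatory stop back under the footnote with the cap.

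Three stronger readings are tempting, and the documents do not support them.

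- A reader might infer a second, shorter stopping point from the most severe row of Table 12: "14 days are allowed to maximize the full effect of anti-hypertensive agents". That sentence is in the antihypertensive-therapy column and concerns optimising those drugs. It fits inside the 3 weeks that the cediranib column of the same row allows.
- A reader might infer that olaparib alone during a cediranib hold breaches Section 3.9: "patients are not allowed to remain in the study if they are taking either cediranib or olaparib as monotherapy". That sentence concerns discontinuation. Section 6.8 and Table 11, footnote a, expressly allow one drug to be held while the other continues.
- A reader might infer that olaparib-only time is simply credited to the combination. SAP 4.2.6 reports combination exposure in two ways. The first counts only interruptions of both drugs; the second counts an interruption of either.

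**Conclusion.** The contradiction stands. The protocol gives a 3-week maximum hold in Section 6.8, Table 11 and Table 12, and allows a longer one in the text of Section 6.8.3.1. It does not say in Table 12 what follows if Grade 1 is not reached, and it words the mandatory stop in two ways, neither with a duration. This rests on reading the current text as written, with no statement of which section takes precedence.

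The number of patients affected is unknown. A reader might take the 41% rate of grade 3 or 4 hypertension with the combination (Section 1.1.4.3) and apply it to 60 patients. That rate is the incidence of the event in a platinum-sensitive population given olaparib capsules, not the share of patients held beyond 3 weeks. Table 12 also tries several antihypertensive drugs before most holds. The documents give no figure for holds past day 21.

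The effect on results is limited to TDT, which is a descriptive secondary endpoint in a single-arm study, and to the exposure and interruption summaries. No effect on the primary ORR is shown. The point merits correction mainly because it concerns a stopping rule for a toxicity that the protocol treats as potentially life-threatening.

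**What to change.** Reconcile Section 3.9 (and the matching list in the synopsis), Section 6.8, Section 6.8.2 with Table 11 footnote a, the text of Section 6.8.3.1 and both Table 12 rows, so that the following read the same throughout:

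- the maximum cediranib hold for hypertension, or an explicit statement that hypertension is an exception to the general limit;
- the action when that limit is reached without recovery;
- the condition for mandatory discontinuation, including whether a prior dose reduction is part of it;
- whether cediranib alone or both drugs stop.

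Which rule to adopt is for the sponsor to decide; this review does not favour one. The cost is protocol wording only: no new data, no change in sample size and no change to the planned analyses.
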